4.1. Intent-to-Treat	4
4.2. Definition of Sub-Group Population in Different Analyses	4
5. Trial Endpoints	4
5.1. Primary Endpoints	4
5.2. Secondary Endpoints	5
5.3. Exploratory Endpoint	5
5.4. Safety Endpoints	5
6. Statistical Analysis	5
6.1. General Approach	5
6.2. Describing the Study Population	5
6.3. Primary Endpoint Analysis	6
6.3.1. Primary Analysis	6
6.3.2. Secondary Analysis	6
6.4. Secondary Endpoint Analysis	6
6.5. Exploratory Endpoint Analysis	6
6.6. Subgroup Analyses	7
6.7. Safety	8
6.8. Missing Data	8
6.9. Interim Analyses	8
6.9.1. Interim Analysis for Sample Size Re-estimation (see above)	8
6.9.2. Interim Analysis Blinded to Investigators	8
References	9

1. Introduction

This document will serve as the Statistical Analysis Plan for CENIC 2 Project 1, entitled “Impact of Very Low Nicotine Content Cigarettes in a Complex Marketplace”. This document describes the planned statistical analysis for evaluating the impact of very low nicotine content cigarettes (VLNC) vs. normal nicotine content (NNC) in a complex marketplace. Details for the proposed analysis of the primary, secondary and other endpoints are provided.

2. Trial Objectives

The overall goal of this project is to determine pattern of product purchase and use when very low (0.4 mg/g) vs. normal nicotine (15.8 mg/g) content cigarettes are available in the marketplace. All participants will have access to non-combustibles (e.g., conventional smokeless tobacco, snus, e-cigarettes, medicinal nicotine) in addition to the study cigarettes, but no access to other combustible, non-study products (e.g., little cigars, cigarillos). The primary aim is to examine the effects of cigarettes that vary in nicotine content on the number of cigarettes smoked and days abstinent from combustible tobacco products in the context of a marketplace with alternative nicotine-containing products. The secondary aims are to examine the characteristics of products alternative to cigarettes that are chosen and to better understand responses to these various products.

3. Trial Design

This is a randomized, multi-center, non-blind study design. 700 subjects will be recruited from 3 study sites and randomized to one of two conditions:

1) very low nicotine content (VLNC) cigarettes with access to non-combusted tobacco/nicotine products; or 2) normal nicotine content (NNC) cigarettes with access to non-combusted tobacco/nicotine products. The two conditions will be referred as the VLNC and NNC groups, respectively, hereinafter.

Participants will undergo three experimental phases in the study: Phase 1: two weeks of baseline; Phase 2: two weeks of usual cigarette marketplace, where subjects will have access to their usual brand cigarettes and non-combusted tobacco/nicotine products; and Phase 3: 12 weeks’ study cigarette market place, where subjects will have access to study cigarettes along with non-combusted tobacco/nicotine products.

3.1. Randomization

Subjects will be randomized at the end of Phase 2 with a 1:1 ratio to the two studied conditions described above. Randomization will be stratified by site using a blocked randomization scheme with random block sizes of 2, 4, and 6. We anticipate no or less than minimal block effects in our data based on previous studies with similar design.

3.2. Sample Size

Sample size was re-estimated for this project by [name] on 8/21/2019. After discussion with members of the CENIC External Advisory Board and representatives of the National Institute of Drug Abuse and Food and Drug Administration, we changed the sample size from 700 to 500.

More power analysis was performed on 11/10/2021 for 2 smaller sample sizes (N = 450 and 400), with all the other parameters being the same as the power analysis performed on 8/21/2019.

We will enroll at least 400 rather than the 700 subjects originally proposed (200 per group) to the study and assume a 20% attrition rate over the 12-week post randomization period. Power analysis was performed for two of the primary outcomes in the primary aim: CPD smoked at the end of Phase 3 and smoke-free days during Phase 3.

3.2.1 Methods: See Section 6.9 for interim analysis and the methods for the sample size re-estimation.

3.2.2 Parameters based on interim data analysis

Table 1. Estimated Parameters Based on Interim Data

	Standard deviation (SD) of CPD of the pooled sample	Rate of abstinence of the control group
Overall	9.62	5.04%
By Gender		
Female (44.7%)	8.84	4.52%
Male (55.3%)	10.41	5.48%
By Age (years)		
18-24 (0.2%)	Not estimable due to the small sample size	No data
25-44 (53.4%)	10.20	2.85%
>=45 (44.7%)	8.95	8.04%

3.2.3 Power re-estimation

The power re-estimation is based on a total of 500, 450, and 400 enrolled subjects with a 20% attrition rate over the 12-week post randomization period. Power analysis was performed for the two primary outcomes: CPD smoked at the end of Phase 3 and smoke-free days during Phase 3. The effect of the two primary outcomes was assumed to be the same as previously assumed: 7 and 15 mean CPD for the VLNC and NNC group; and a 11 day difference (we assumed 12 abstinence days vs. 1 abstinence day, out of 84 days, previously) in the smoke-free days for VLNC vs. NNC. The nuisance parameters were based on the interim analysis (see Section 6.9 and Table 1 above).

The two-sided type-I error rate for each outcome (CPD and abstinence) was set at $\alpha=0.025$ ($=0.05/2$ outcomes by the Bonferroni method) for the overall sample as previously designed. The type I error rate for the gender subgroup analysis was set to be α divided by the number of subgroups ($=2$) as previously designed. The type I error rate for the age subgroup analysis was set to be α divided by 2, rather than 3 because based on the interim data, there were <1% of participants in the 18-24 age group, hence, this age group was dropped from the power analysis. The Subgroup Analysis section (Section 6.6) in the SAP was revised accordingly.

The same statistical methods were used as previously designed. Specifically, t-test was used for the CPD outcome. For the smoke-free days outcome, we first calculated the rate of smoke-free days by dividing the number of smoke-free days by the total number of days in Phase 3 (84 days) and then used z-test for the Poisson rate difference. PASS 14 was used for power calculations.

The estimated power for 500, 450, and 400 subjects is presented in Table 2.

Table 2. Power Analysis for Total Enrolled N=500, 450, and 400

Primary outcomes	VLNC	NNC	Overall sample	³ Subgroup analysis by sex		⁴ Subgroup analysis by age		
				F	M	18-24	25-44	45+

N enrolled = 500								
¹ Cigarettes (study or non-study) per day smoked at the end of Phase 3 (calculated as mean CPD based on 7 days' IVR data before the week 12 visit)	7	15	>.99	>.99	>.99	-	>.99	>.99
² Number of smoke-free days during Phase 3 (12 weeks or 84 days)	11 days difference		.94	.55	.61	-	.72	.41
N enrolled = 450								
¹ Cigarettes (study or non-study) per day smoked at the end of Phase 3 (calculated as mean CPD based on 7 days' IVR data before the week 12 visit)	Same as above	>.99	>.99	>.99	-	>.99	>.99	
		.92	.49	.56	-	.67	.37	
N enrolled = 400								
¹ Cigarettes (study or non-study) per day smoked at the end of Phase 3 (calculated as mean CPD based on 7 days' IVR data before the week 12 visit)	Same as above	>.99	>.99	>.99	-	>.99	>.99	
		.88	.43	.50	-	.61	.32	

¹We assumed an equal SD for the two treatment arms. See Table 1 (left panel) for SD for the overall group, by gender, and by age.

²The NNC arm's rate of abstinence was based on the interim analysis result (see Table 1, right panel).

³44.7% female and 55.3% male, based on the interim data (see Table 1).

⁴0.2%, 53.4%, and 44.7% for 18-24, 25-44, and \geq 45 years old, respectively, based on the interim data (see Table 1).

4. Study Populations

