16.3. Sample Size

We will enroll 400-450 subjects (approximately 200-225 per group) to the study and assume a 20% attrition rate over the 12-week post randomization period. Power analysis was performed for two of the primary outcomes in the primary aim: CPD smoked at the end of Phase 3 and smoke-free days during Phase 3. The effect sizes and the distribution of population demographics were projected from a pilot study (U19CA157345; Hatsukami et al., 2017) and Donny et al. (2015)^{16,14}. The two-sided type-I error rate for each outcome (CPD and smoke-free days) was set at $\alpha=0.025$ ($=0.05/2$ outcomes by the Bonferroni method) for the overall sample. Powers for two independent subgroup analyses, by sex or by age, are also presented in Table 1, with type I error rate equal to α divided by the number of subgroups ($=2$) for each factor. T-test was used for the CPD outcome. For the smoke-free days outcome, we first calculated the rate of smoke-free days by dividing the number of smoke-free days by the total number of days in Phase 3 (approximately 84 days) and then used z-test for the Poisson rate difference. PASS 13 was used for power calculations.

Table 1: Power Analysis for Total Enrolled (randomized) N=450 and 400

Primary outcomes	VLNC	NNC	Overall sample	³ Subgroup analysis by sex		⁴ Subgroup analysis by age		
				F	M	18-24	25-44	45+
N enrolled = 450								
¹ Cigarettes (study or non-study) per day smoked at the end of Phase 3 (calculated as mean CPD based on 7 days' IVR data before the week 12 visit)	7	15	>.99	>.99	>.99	-	>.99	>.99
² Number of smoke-free days during Phase 3 (12 weeks or 84 days)	11 days difference		.92	.49	.56	-	.67	.37
N enrolled = 400								
¹ Cigarettes (study or non-study) per day smoked at the end of Phase 3 (calculated as mean CPD based on 7 days' IVR data before the week 12 visit)	Same as above		>.99	>.99	>.99	-	>.99	>.99
² Number of smoke-free days during Phase 3 (12 weeks or 84 days)			.88	.43	.50	-	.61	.32

¹We assumed an equal SD for the two treatment arms. See Table 1 (left panel) in SAP for SD for the overall group, by gender and by age.

² The NNC arm's rate of abstinence was based on the interim analysis result (see Table 1 in SAP, right panel).

³44.7% female and 55.3% male, based on the interim data (see Table 1 in SAP).

⁴0.2%, 53.4%, and 44.7% for 18-24, 25-44, and \geq 45 years old, respectively, based on the interim data (see Table 1 in SAP).

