6.3.1. Primary Analysis

We expect the two groups to, on average, be balanced for important baseline characteristics due to randomization, so the primary analyses will be regressions for the difference in CPD and the number of smoke-free days between two conditions, adjusting for only the baseline value (the mean CPD and the percent of smoke-free days during Phase 2, respectively). Specifically, for the CPD outcome at week 12, we will use linear regression; for the number of smoke-free days, we will use Poisson regression or negative binomial regression when there is over-dispersion in the count data.

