6.9. Interim Analyses

6.9.1. Interim Analysis for Sample Size Re-estimation (see above)

One interim analysis was conducted for sample size re-estimation. Nuisance parameters were estimated based on non-comparative data, whereas the significance level, the desired power, and the assumed targeted difference in outcome due to treatment assignment were not changed. In general, sample size re-estimations based on non-comparative data are expected to have a negligible effect on the Type I error (USDHHS, FDA, CDER, and CBER, 2018).

First, we calculated the distribution of gender and age (18-24, 25-44, and ≥ 45 years old). For the outcome of CPD, we calculated the variance for the pooled sample. For the outcome of cigarette abstinence, we evaluated the control (NNC) group’s average rate of abstinence, which is calculated as the total number of smoke-free days observed among randomized participants divided by the total number of IVR days during Phase 3 (12 weeks).

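### The smoke-free-day powers match one day of exposure per person instead of 84, and no dispersion is given for the planned count model

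*Combined protocol and SAP*

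**What the plan says.** SAP 3.2.3 keeps the assumed difference at 11 smoke-free days. It says the days were divided "by the total number of days in Phase 3 (84 days) and then used z-test for the Poisson rate difference". Protocol 16.3 describes the same calculation. The control rate comes from interim data: footnote 2 of SAP Table 2 says that the NNC "rate of abstinence was based on the interim analysis result (see Table 1, right panel"). SAP 6.9.1 defines that rate; it is "calculated as the total number of smoke-free days observed among randomized participants divided by the total number of IVR days during Phase 3". It is therefore a rate per day. Neither document states the exposure per person that was entered in the power software.

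SAP 3.2 describes how the smaller sizes came to be covered: "More power analysis was performed on 11/10/2021 for 2 smaller sample sizes (N = 450 and 400"), with the other parameters unchanged.

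The planned primary analysis of the endpoint is different. In SAP 6.3.1, "we will use Poisson regression or negative binomial regression when there is over-dispersion in the count data", with the Phase 2 value as the only covariate. On what the interim data supplied, SAP 6.9.1 says: "For the outcome of CPD, we calculated the variance for the pooled sample". For abstinence it describes only the control group's average rate. No variance, dispersion or within-person correlation of smoke-free days appears in either document.

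**The concern.** A rate per day has to be paired with the number of days each person is observed. An 11-day difference in 84 days, with 160 or more completers per arm, should give a Poisson rate test almost complete power. The table instead shows .88 to .94 overall and .32 to .72 in the subgroups, which suggests that the 84 days dropped out of the calculation.

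CPD power is above .99 in every cell, so the smoke-free-day rows are the only informative power figures for the current 400-450. If they do not follow from the stated method, a report that repeats them would misstate the trial's power for a primary endpoint. They would be no better as a guide to the planned model, whose power depends on a dispersion that is not given.

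**Working it through.** **Inputs.**
- Difference d = 11/84 = 0.13095 per day (SAP 3.2.3).
- Control rate l1 and sample share (SAP Table 1): overall 5.04%; female 4.52%, share 44.7%; male 5.48%, 55.3%; age 25-44 2.85%, 53.4%; age 45+ 8.04%, 44.7%.
- VLNC rate l2 = l1 + d.
- Attrition 20% and 1:1 allocation (SAP 3.2.3, 3.1), so n per arm = 0.8 × N × share / 2.
- Two-sided alpha 0.025 overall (z = 2.241) and 0.0125 in subgroups (z = 2.498).
- Exposure t days per person: not stated.

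**Formula** (z-test for a difference of Poisson rates, unpooled variance): power = Φ( d / √[(l1 + l2)/(n·t)] − z ).

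**Reproducing the printed values, t = 1.** For N=400 overall, n = 160 and l1 + l2 = 0.0504 + 0.1814 = 0.2318. The standard error is √(0.2318/160) = 0.0381, d/SE = 3.441, and power = Φ(3.441 − 2.241) = 0.885. All cells:

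| N | | Overall | F | M | 25-44 | 45+ |
|---|---|---|---|---|---|---|
| 500 | printed | .94 | .55 | .61 | .72 | .41 |
| | t = 1 | .946 | .553 | .622 | .734 | .419 |
| 450 | printed | .92 | .49 | .56 | .67 | .37 |
| | t = 1 | .920 | .500 | .566 | .679 | .373 |
| 400 | printed | .88 | .43 | .50 | .61 | .32 |
| | t = 1 | .885 | .443 | .505 | .616 | .327 |

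The largest gap over the 15 cells is 0.014. If d is rounded to 0.13, the N=400 row becomes .881/.438/.500/.611/.323 and the largest gap is 0.009. At t = 1, five variants (square-root scale, log rate ratio, one-sided test, no attrition, two proportions) do not come within 0.02 of the printed value in any cell.

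**Other exposures.** At t = 2 the N=400 row is .996/.797/.854/.927/.656, already far from the printed one. At t = 84 every cell exceeds 0.999; for N=400 overall, d/SE = 3.441 × √84 = 31.5.

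**Can t = 1 stand for strong within-person correlation?** Using t = 1 multiplies the 84-day Poisson variance by 84, so the implied SD of the count is 84√p. The largest SD of a 0-84 count with mean 84p is 84√[p(1−p)], reached when everyone is smoke-free on all days or on none.

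| Arm | p | Implied SD (days) | Largest possible SD (days) |
|---|---|---|---|
| NNC | .0504 | 18.9 | 18.4 |
| VLNC | .1814 | 35.8 | 32.4 |

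Replacing p by p(1−p) in the formula gives the z-test on the mean difference at the largest possible variance:

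| N | Overall | F | M | 25-44 | 45+ |
|---|---|---|---|---|---|
| 450 | .958 | .583 | .656 | .756 | .459 |
| 400 | .933 | .522 | .593 | .696 | .405 |

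Every value is above the printed one.

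**Planned model, illustration only.** The documents give no correlation, so it is assumed here. The data are beta-binomial days out of 84 at N=400, without the baseline covariate.

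| Test | Assumed correlation | Overall | F | M | 25-44 | 45+ |
|---|---|---|---|---|---|---|
| Log rate ratio, empirical variance | 0.8 | .97 | .51 | .63 | .70 | .42 |
| | 0.5 | >.99 | .82 | .89 | .94 | .70 |
| | 0.3 | >.99 | .97 | .99 | >.99 | .92 |
| Negative binomial, model-based Wald | 0.8 | .71 | .25 | .24 | .43 | .11 |

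With equal arm means the empirical-variance test rejects close to its nominal level (0.022-0.027 overall, 0.009-0.016 in subgroups). The model-based test at 0.8 rejects only 0-0.15% of the time, against a nominal 2.5% overall and 1.25% in subgroups. Its low values are therefore not an estimate of the trial's power. They show how much the choice of standard error matters.

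**The case against.** The exposure entered is not stated, so the table may be a correct calculation under a very cautious assumption, with one unit per person standing in for correlated days. On that view, calling it wrong treats 84 independent days as what the SAP meant. The >0.999 benchmark is one that nobody should adopt, and at the largest-variance bound the overall gap is only 4 to 5 points. Powering on a simpler test than the final model is common, and SAP 6.3.1 already provides for over-dispersion in the analysis. The listed enrolment period ended on 9/30/2022, before the last SAP modification on 11/21/2022, so a new figure cannot change recruitment.

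Parts of this stand. One day is inferred from the match. The bound is the informative comparison. Direction under the planned model is open. The simulated correlations are assumptions. Recruitment will not change.

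The defence of deliberate caution does not stand. Neither document states such an assumption, and it would need more variance than a 0-84 count can have in either arm. No admissible variance at the stated means takes the difference test down to the printed values. Naming a simpler test for power is acceptable, but the figures must then follow from that test.

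**Conclusion.** The concern holds. For the stated test, the smoke-free-day powers in SAP Table 2 and protocol Table 1 are too low. At N=400 the understatement is at least about 5 points overall (.933 against .88) and 8 to 9 points in the subgroups. At N=450 it is about 4 points overall and 9 to 10 in the subgroups. With less than the extreme variance the understatement is larger. This rests on the SAP's own rates, shares, alphas and attrition, and on an 84-day Phase 3 for each completer.

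For the planned regression the table says nothing usable, because neither the dispersion nor the type of standard error (model-based or robust) is stated. Power there could lie on either side of the printed values. This is a correction to a stated figure. It neither shows underpowering nor challenges the sample size, and CPD power is unaffected. The subgroup cells matter less, since SAP 6.6 treats subgroups as checks of consistency.

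**What to change.** Recompute the smoke-free-day rows of SAP Table 2 and protocol Table 1 for the planned count model. Use 84 days per person and the unchanged 11-day target. Estimate over-dispersion from Phase 3 data pooled over the arms and show power over a range around it. This keeps to the principle already in SAP 6.9.1: "Nuisance parameters were estimated based on non-comparative data". State beside the table the exposure used and whether the standard error is model-based or robust. Do not simply replace the entries with >0.999, which would assume 84 independent days per person.

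The cost is one pooled dispersion estimate, one recalculation, and edits to the smoke-free-day rows of two tables. Enrolment, alpha, endpoints and the analysis model do not change.

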4.1. Intent-to-Treat

The primary analysis of all endpoints will adhere to the intent-to-treat principle. Under this principle, all randomized subjects will be included in the analysis in the group to which they were randomized regardless of protocol violations and compliance to treatment assignment.

4.2. Definition of Sub-Group Population in Different Analyses

We intend to complete pre-planned subgroup analyses by sex, age groups (18-44, and 45+), and whether the participant was recruited pre- or post-COVID. Subgroup analysis will allow us to evaluate the consistency of the effect of VLNC vs. NNC across important subgroups.

5. Trial Endpoints

5.1. Primary Endpoints

- Cigarettes per day (CPD): the mean cigarettes (study and non-study cigarettes) smoked per day based on 7 days' Daily Interactive Voice Response (IVR)-Revised (corrected with participant for errors) data before the week 12 visit.
- Smoke-free days during Phase 3: the number of days not smoking any combustible products based on IVR-Revised.

